### **7.1.3 Respiratory stopping criteria**

Discontinuation of study intervention is required by the investigator when a participant with respiratory disease meets the condition below:

- Exacerbation of known respiratory disease that requires hospital admission.
- Note: If any respiratory problems arise such as ongoing infection (for example, bronchitis, bronchiolitis or mild pneumonia, or acute dyspnea due to new onset arrhythmia), or change in respiratory medications is needed, to include, starting, or an increase in frequency of use of inhaler therapy, it is up to the Investigator to determine whether the participant may remain in the study whilst adjusting the other therapies or to permanently discontinue the participant from the study intervention.

## **7.2 Participant Discontinuation/Withdrawal from the Study**

Discontinuation of the participant from the study by the investigator:

- A participant may be discontinued from the study at any time at the discretion of the investigator for safety, behavioral, compliance, or administrative reasons.
- At the time of discontinuing from the study, if the participant has not been discontinued from the study intervention, see Section 7.1.

Voluntary withdrawal from the study by the participant:

- A participant may withdraw from the study at any time at the participant's own request for any reason (or without providing any reason).
- A participant who wishes to withdraw from the study must be informed by the investigator about modified follow-up options (eg, telephone contact, a contact with a relative or treating physician, or information from medical records).
- If the participant withdraws consent for disclosure of future information, the Sponsor may retain and continue to use any data collected before such a withdrawal of consent.
- If the participant withdraws from the study, the Sponsor may retain and continue to use any samples collected before such a withdrawal of consent for the purposes the participant originally consented unless the participant withdraws consent for use of samples already collected. If the participant specifically withdraws consent for any use of samples, it must be documented in the site study records by the investigator and the investigator must inform the Local and Global Study Team. Destruction of any samples taken and not yet tested should be carried out in line with documented sample withdrawal wishes in conjunction with what was stated in the informed consent and local regulation.

### **7.3 Lost to Follow-up**

A participant will be considered lost to follow-up if the participant repeatedly fails to return for scheduled visits and is unable to be contacted by the study site.

The following actions must be taken if a participant fails to return to the study site for a required study visit:

- The site must attempt to contact the participant and reschedule the missed visit as soon as possible. The participant should be counseled on the importance of maintaining the assigned visit schedule. At this time ascertain whether the participant should or wishes to or continue in the study.
- Before a participant is deemed lost to follow-up, the investigator or designee must make every effort to regain contact with the participant (where possible, 3 telephone calls, texts, emails, and if necessary, a certified letter to the participant's last known mailing address or local equivalent methods). These contact attempts should be documented in the participant's medical record.
- Should the participant continue to be unreachable, the participant will be considered to have been lost to follow-up.

## **8 STUDY ASSESSMENTS AND PROCEDURES**

- Study procedures and their timing are summarized in the SoA (Section 1.2). Protocol waivers or exemptions are not allowed.
- Urgent safety concerns should be discussed with the investigator upon occurrence or awareness to determine if the participant should continue or discontinue study intervention.
- Adherence to the study design requirements, including those specified in the SoA, is essential and required for study conduct.
- All screening evaluations must be completed and reviewed to confirm that potential participants meet all eligibility criteria. The investigator will maintain a screening log to record details of all participants screened and to confirm eligibility or record reasons for screening failure, as applicable.
- Procedures conducted as part of the participant's routine clinical management (eg, blood count) and obtained before signing of the ICF may be utilized for screening or baseline purposes provided the procedures met the protocol-specified criteria and were performed within the time frame defined in the SoA.
- Instructions for the collection and handling of HBS will be provided in the study-specific laboratory manual. Samples should be stored in a secure storage space with adequate measures to protect confidentiality. For further details on handling of HBS see [Appendix C](#).

In the event of a significant study-continuity issue (eg, caused by a pandemic), alternate strategies for participant visits, assessments, medication distribution and monitoring may be implemented by the Sponsor or the investigator, as per local health authority/ethics requirements.

Laboratory and analyte results that could unblind the study will not be reported to investigative sites or other blinded personnel until the study has been unblinded.

The approximate amount of blood collected from each participant over the duration of the study is around 300ml (approximately 20 tablespoons), and the maximum amount of blood collected from each participant over the duration of the study, including any extra assessments that may be required, will not exceed 500 mL (approximately 33 tablespoons). Repeat or unscheduled samples may be taken for safety reasons or for technical issues with the samples.

## 8.1 Efficacy Assessments

Planned timepoints for all efficacy assessments are provided in the SoA (Section 1.2).

Laboratory efficacy variables are shown in Table 5.

**Table 5 Laboratory Efficacy Variables**

Primary endpoint	Secondary endpoints

Percent change from baseline of LDL-C at Week 12 (in “ideal” scenarios where intercurrent events would not occur)

	

Percent change from baseline of LDL-C at Week 12 (in “real-world” conditions)

Percent change from baseline at Week 12 (in “ideal” scenarios) in:

Total cholesterol

HDL-C

Triglycerides

Non-HDL-C

VLDL-C*

ApoA1

ApoB

Lp(a)

Remnant cholesterol*

hsCRP

Percent change from baseline at Week 12 (in “real-world” conditions) in:

Total cholesterol

HDL-C

Triglycerides

Non-HDL-C

VLDL-C*

ApoA1

ApoB

Lp(a)

Remnant cholesterol*

hsCRP

\* Calculated from standard lipid profile.

ApoA1 = apolipoprotein A-1; ApoB = apolipoprotein B-100; HDL-C = high-density lipoprotein cholesterol; hsCRP = high-sensitivity C-reactive protein; LDL-C = low-density lipoprotein cholesterol; Lp(a) = lipoprotein (a); VLDL-C = very-low-density lipoprotein cholesterol.

## **8.2 Safety Assessments**

Planned time points for all safety assessments are provided in the SoA (Section 1.2).

Immediate safety concerns should be discussed with the Sponsor immediately upon occurrence or awareness to determine if the participant should continue or discontinue study intervention.

### **8.2.1 Physical Examinations**

A complete physical examination will be performed and include assessments of the following; general appearance, respiratory, cardiovascular, abdomen, skin, head and neck (including ears, eyes, nose, and throat), lymph nodes, thyroid, musculoskeletal (including spine and extremities), and neurological systems.

A brief physical examination will include, at a minimum, assessments of the skin, lungs, cardiovascular system, and abdomen (liver and spleen).

New or worsening abnormalities may qualify as AEs; see Section [8.3](#) for details

Height will be assessed using locally available tools without the participant wearing shoes. Weight will be assessed using the same scale (properly maintained and calibrated), and with the participant wearing a similar amount of clothes (eg, underwear only or light indoor clothing only) at each time.

Physical examination will be performed at timepoints as specified in the SoA (Section [1.2](#)).

### **8.2.2 Vital Signs**

Vital signs will be performed at timelines as specified in the SoA (Section [1.2](#)). Vital signs will be assessed before any interventional study procedures (blood sampling, ECG, IMP administration). The participant should be in a resting, seated position for at least 5 minutes prior to the collection of vital sign, as follow:

- Body temperature (measured in Celsius). Oral measurement is preferred, but other methods are acceptable as per local standards of care
- Heart (pulse) rate
- Respiratory rate
- Oxygen saturation ( $SpO_2$ ) measured by pulse oximetry
- Blood pressure (systolic and diastolic)

Blood pressure and pulse measurements should be taken by an adequately trained health care professional and assessed with a completely automated device (a calibrated sphygmomanometer is preferred). If not available, another device calibrated carefully in

proportion to a mercury sphygmomanometer should be used. The use of aneroid manometers should be avoided. An appropriate cuff size must be used to ensure accurate measurement. The disappearance of sound (Korotkov Phase V) should be used for the diastolic reading.

Blood pressure and pulse measurements should be assessed with the participant rested in a seated position, their back supported and feet on the ground. Three consecutive blood pressure and pulse readings should be recorded at intervals of at least 2 minutes. The average of the SBP, DBP and pulse readings should be recorded in the eCRF.

### **8.2.3      Electrocardiograms**

12-lead ECG will be performed at timepoints as specified in the SoA (Section [1.2](#)).

All 12-lead ECGs will be obtained in triplicate with no more than a 5-minute interval between each reading using a properly maintained and calibrated machine. The mean value from the three ECG readings will be recorded in the eCRF. The recordings should be done after the participant has been lying down to rest for at least 10 minutes. For participants with pacemakers, ECG variables should be read manually. ECGs may also be performed according to clinical judgment or as indicated based on any symptoms or clinical events (eg, cardiac arrhythmia).

The following ECG parameters should be collected: PR interval, RR interval, QRS duration, QT and QTcF intervals, and heart rate. An overall evaluation of the ECG results should also be performed.

### **8.2.4      Clinical Safety Laboratory Tests**

Blood and urine samples for determination of clinical chemistry, haematology, coagulation, and urinalysis will be taken at the visits indicated in the SoA (Section [1.2](#)).

The clinical chemistry, hematology, coagulation, and urinalysis will be performed at a central laboratory. Sample tubes and sample sizes will be described in the Laboratory Manual.

Additional safety samples may be collected if clinically indicated at the discretion of the investigator.

Drugs of abuse screening will be performed at a central laboratory, unless the investigator performs these locally per each study site's guidelines.

The following laboratory variables will be measured ([Table 6](#)).

**Table 6** **Laboratory Safety Variables**

Hematology/Hemostasis/Glycaemic control
 
 
• Blood 
 
○ Hematocrit
 
○ Hb
 
○ Leukocyte count
 
○ Leukocyte differential count (absolute count)
 
○ MCV
 
○ MCH
 
○ MCHC
 
○ Platelet count
 
○ RBC
 
○ Reticulocyte absolute count
 
○ Coagulation
 
○ HbA1C
 
 
 
 
Urinalysis
 
 
• Microscopy including white blood cell/RBC and casts
 
• Urine 
 
○ Appearance and color
 
○ Urobilinogen
 
○ Blood
 
○ Glucose
 
○ Ketones
 
○ Leukocytes
 
○ Nitrites
 
○ pH
 
○ Protein
 
○ Specific gravity
 
 
 
• Urine renal safety biomarkers 
 
○ Albumin
 
○ Creatinine
 
○ eGFR
 
○ Total protein
 
 
 
	
Clinical Chemistry
 
 
• Plasma/Serum 
 
○ Albumin
 
○ ALP
 
○ ALT
 
○ AST
 
○ Bilirubin, total
 
○ Bicarbonate
 
○ Blood urea nitrogen
 
○ Creatinine
 
○ GGT
 
○ High sensitivity CRP
 
○ Potassium
 
○ Sodium
 
○ Total Protein
 
 
 
 
Endocrinology
 
 
• Serum 
 
○ FSH (women only, at screening)
 
○ LH (women only, at screening)
 
 
 
 
Pregnancy Dipstick Test
 
 
• Pregnancy test (urine human chorionic gonadotropin)a
 
 
Viral Serology (screening only)
 
 
• HIV I
 
• HIV II
 
• HBsAg
 
• Hepatitis C virus antibody
 

--	--

ALP = alkaline phosphatase; ALT = alanine aminotransferase/transaminase; AST = aspartate aminotransferase/transaminase; CRP = C-reactive protein; eGFR = estimated glomerular filtration rate; FSH = follicle stimulating hormone; GGT = gamma glutamyl transpeptidase; Hb = hemoglobin; HIV = human immunodeficiency virus; HBsAg = hepatitis B surface antigen; LH = luteinizing hormone; MCH = mean corpuscular hemoglobin; MCHC = mean corpuscular hemoglobin concentration; MCV = mean corpuscular volume; RBC = red blood cell.

aConfirmatory serum test analyzed at the central laboratory is indicated if local urine pregnancy test is positive at visit 1.

In case a participant shows an AST or ALT  $\geq 3 \times$  ULN together with TBL  $\geq 2 \times$  ULN please refer to [Appendix E](#), for further instructions.

### **8.3 AEs, SAEs, and Other Safety Reporting**

The Principal Investigator is responsible for ensuring that all staff involved in the study are familiar with the content of this section.

The definitions of an AE or SAE can be found in [Appendix B](#).

Participants (or, when appropriate, a caregiver, surrogate, or the participant's legally authorized representative) will notify the investigator or designees of symptoms. These must then be assessed by the investigator and if considered an AE it will be reported by the investigator.

The investigator and any designees are responsible for detecting, documenting, and recording events that meet the definition of an AE.

#### **8.3.1 Time Period and Frequency for Collecting AE and SAE Information**

Adverse Events will be collected from time of first dose, throughout the treatment period, and including the follow-up period.

Serious Adverse Events will be recorded from the time of signing of the ICF.

If the investigator becomes aware of an SAE with a suspected causal relationship to the IMP that occurs after the end of the clinical study in a treated participant, the investigator shall, without undue delay, report the SAE to the Sponsor.

#### **8.3.2 Follow-up of AEs and SAEs**

Any AEs that are unresolved at the participant's last AE assessment in the study are followed up by the investigator for as long as medically indicated, but without further recording in the eCRF. The Sponsor retains the right to request additional information for any participant with ongoing AE(s)/SAE(s) at the end of the study, if judged necessary.

#### **AE variables**

The following variables will be collected for each AE:

- Adverse Event (verbatim). Note: for COVID-19 related events, the investigator should add 'COVID' as part of the verbatim term
- The date and time when the AE started and stopped
- Maximum intensity
- Intensity grading: mild, moderate, or severe
- Whether the AE is serious or not
- Investigator causality rating against the IMP(s) (yes or no)
- Action taken with regard to IMP(s)

- AE caused participant's withdrawal from the study (yes or no)
- Outcome

In addition, the following variables will be collected for SAEs:

- Date AE met criteria for SAE
- Date investigator became aware of SAE
- AE description
- AE is serious due to
- Date of hospitalization
- Date of discharge
- Probable cause of death
- Date of death
- Autopsy performed
- Causality assessment in relation to study procedure(s)
- Causality assessment to other medication

### **8.3.3 Causality Collection**

The investigator should assess causal relationship between IMP and each AE, and answer 'yes' or 'no' to the question 'Do you consider that there is a reasonable possibility that the event may have been caused by the IMP?'

For SAEs causal relationship should also be assessed for other medication and study procedures. Note that for SAEs that could be associated with any study procedure the causal relationship is implied as 'yes'.

A guide to the interpretation of the causality question is found in [Appendix B](#).

### **8.3.4 AEs Based on Examinations and Tests**

Deterioration as compared to baseline in protocol-mandated laboratory values and vital signs, should only be reported as AEs if they meet any of the following:

- Fulfil any of the SAE criteria
- Are the reason for discontinuation of the IMP
- Are clinically relevant as judged by the investigator (which may include but is not limited to consideration as to whether intervention or non-planned visits were required or other action was taken with the IMP, eg, dose adjustment or drug interruption).

If deterioration in a laboratory value/vital sign is associated with clinical signs and symptoms, the sign or symptom will be reported as an AE and the associated laboratory result/vital sign

will be considered as additional information. Wherever possible the reporting investigator uses the clinical, rather than the laboratory term (eg, anemia vs low hemoglobin value). In the absence of clinical signs or symptoms, clinically relevant deteriorations in non-mandated parameters should be reported as AE(s).

Deterioration of a laboratory value, which is unequivocally due to disease progression, should not be reported as an AE/SAE.

Any new or aggravated clinically relevant abnormal medical finding at a physical examination as compared with the baseline assessment will be reported as an AE unless unequivocally related to the DUS.

The results from the protocol mandated laboratory tests and vital signs will be summarized in the CSR.

### **8.3.5 AEs Based on Signs and Symptoms**

All signs or symptoms spontaneously reported by the participant or reported in response to the open question from the study site staff: 'Have you had any health problems since the previous visit/you were last asked?', or revealed by observation will be collected and recorded in the eCRF.

When collecting AEs, the recording of diagnoses is preferred (when possible) to recording a list of signs and symptoms. However, if a diagnosis is known and there are other signs or symptoms that are not generally part of the diagnosis, the diagnosis and each sign or symptom will be recorded separately.

### **8.3.6 Hy's Law**

Cases where a participant shows elevations in liver biochemistry may require further evaluation, and occurrences of  $AST \text{ or } ALT \geq 3 \times ULN$  together with  $TBL \geq 2 \times ULN$  may need to be reported as SAEs. Please refer to [Appendix E](#) for further instruction on cases of increases in liver biochemistry and evaluation of Hy's Law.

### **8.3.7 Disease Progression**

Disease progression can be considered as a worsening of a participant's condition attributable to the disease for which the IMP is being studied. It may be an increase in the severity of the DUS and/or increases in the symptoms of the disease. The development of symptoms of DUS are those which might be expected to occur as a result of dyslipidemia (eg, increase in blood lipid levels) should be considered as disease progression and not an AE. Events, which are unequivocally due to disease progression, should not be reported as AEs during the study.

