### 2.2 Background

#### 2.2.1 Dyslipidemia

Dyslipidemias are alterations to the plasma lipid profile that are often associated with clinical conditions. Hypercholesterolemia due to elevated LDL-cholesterol levels is a common form of dyslipidemia and is a major causal factor for IHD and IS in both the developed and the developing world. Elevated LDL-C can be genetically determined (primary or familial dyslipidemias) or secondary to other conditions (such as diabetes mellitus, obesity or an unhealthy lifestyle), the latter being more common. The global burden of dyslipidemia has increased over the past 30 years ([Pirillo et al 2021](#)). Cardiovascular disease (CVD), principally IHD and IS, is the leading cause of global mortality and a major contributor to disability. Prevalent cases of CVD nearly doubled from 271 million in 1990 to 523 million in 2019, and the number of CVD deaths steadily increased from 12.1 million in 1990, reaching 18.6 million in 2019 ([Pirillo et al 2021](#)). The global trends for disability-adjusted life years and years of lost life also increased significantly due to IHD and IS. Cardiovascular disease burden continues its decades-long rise for almost all countries ([Roth et al 2020](#)). Elevated LDL-C remains the main interventional and pharmacologic target for prevention of CVD ([Pirillo et al 2021](#), [Ference et al 2018](#), [Roth et al 2020](#)).

Statins are the first-line therapy for lowering of LDL-C recommended by the latest dyslipidemia guidelines ([Mach et al 2020](#); [Reiter-Brennan et al 2020](#)). Reduction of LDL-C levels by statins leads to significant reduction in cardiovascular events including coronary artery disease and other cardiovascular related deaths ([Collins et al 2016](#)). However, despite the substantial benefits of statin therapy, many patients do not reach LDL-C target levels. Current guidelines call for LDL-C to be lowered  $\geq 50\%$  with maximally tolerated statins in patients with existing atherosclerotic CVD ([Atar et al 2021](#)). Additional evidence demonstrates that aggressively lowering LDL-C levels to  $< 40$  mg/dL lowers CVD risk in a wider range of patients ([Marston et al 2021](#)). This underscores the medical need for developing new cost-effective LDL-C lowering medicines to achieve the most recent dyslipidemia guidelines for primary and secondary prevention of CVD.

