### **8.3.8 Disease Under Study**

Symptoms of DUS are those which might be expected to occur as a direct result of dyslipidemia. Events which are unequivocally due to DUS should not be reported as AEs during the study unless they meet SAE criteria or lead to discontinuation of the IMP.

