### **8.3.9 Reporting of SAEs**

All SAEs must be reported whether or not considered causally related to the IMP. All SAEs will be recorded in the eCRF.

If any SAE occurs during the study, investigators or other site personnel will inform the appropriate Sponsor representatives within one day, ie, immediately but **no later than 24 hours** of when he or she becomes aware of it.

The designated Sponsor representative will work with the investigator to ensure that all the necessary information is provided to the AstraZeneca Patient Safety data entry site **within one calendar day** of initial receipt for fatal and life-threatening events **and within 5 calendar days** of initial receipt for all other SAEs.

For fatal or life-threatening AEs where important or relevant information is missing, active follow-up will be undertaken immediately. Investigators or other site personnel will inform the Sponsor representative of any follow-up information on a previously reported SAE within one calendar day, ie, immediately but **no later than 24 hours** of when he or she becomes aware of it.

Once the investigators or other site personnel indicate an AE is serious in the Electronic Data Capture (EDC) system, an automated email alert is sent to the designated Sponsor representative.

If the EDC system is not available, then the investigator or other study site staff reports the SAE via secure method to the appropriate Sponsor representative.

When the EDC is temporarily not accessible, the Sponsor Study Representative should confirm that the investigator/site staff enters the SAE in the AstraZeneca EDC when access resumes.

For further guidance on the definition of an SAE, see [Appendix B](#).

The reference document for definition of expectedness/listedness is the IB for the AstraZeneca IMP.

In the European Union, the Sponsor will comply with safety reporting requirements and procedures as described in the European Clinical Trials Regulation (EU) No 536/2014. All suspected unexpected serious adverse reactions (SUSARs) to investigational medicinal product will be reported to the EudraVigilance database within the required regulatory timelines.

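### Protocol 8.3.7 and 8.3.4 exclude disease-progression events from reporting without the serious-event exception in 8.3.8, so sites could report serious events inconsistently

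*Protocol*

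**What the plan says.** Four neighbouring parts of Protocol 8.3 bear on an event attributed to dyslipidemia.

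- **8.3.7 Disease Progression** describes progression as worsening of the condition for which the IMP is studied: "It may be an increase in the severity of the DUS and/or increases in the symptoms of the disease". Its one example is a lipid rise ("eg, increase in blood lipid levels) should be considered as disease progression and not an AE"). It closes with the general rule: "Events, which are unequivocally due to disease progression, should not be reported as AEs during the study".
- **8.3.8 Disease Under Study** says that events unequivocally due to that disease "should not be reported as AEs during the study unless they meet SAE criteria or lead to discontinuation of the IMP".
- **8.3.4 AEs Based on Examinations and Tests** first lists laboratory and vital-sign deterioration that is reportable, including changes that meet an SAE criterion or are the reason for stopping the IMP. It later adds: "Deterioration of a laboratory value, which is unequivocally due to disease progression, should not be reported as an AE/SAE".
- **8.3.9 Reporting of SAEs** says: "All SAEs must be reported whether or not considered causally related to the IMP".

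Appendix B 2 defines an SAE as an AE that fulfils at least one seriousness criterion. SAP 4.6.2.1 counts participants with at least one reported serious AE.

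**The concern.** For a serious event that an investigator attributes to dyslipidemia, these sections do not give one answer. Section 8.3.7 says not to report it, while 8.3.8 and 8.3.9 say to report it. The general duty in 8.3.9 does not clearly settle the matter, because it covers SAEs and an SAE must first be an AE.

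What is at stake is the completeness of the SAE data. Protocol 9.2 says the sample size is driven by safety and tolerability and is meant to provide a robust safety database. If two sites resolve the wording differently, the same event enters the SAE tables at one and not at the other. Individual case reporting to the sponsor is affected in the same way.

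**Working it through.** This is a comparison of wording. The plan states no figure on this point, so there is none to reproduce.

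**Step 1: do the sections cover the same events?** Largely, yes. Section 8.3.7 defines progression through greater severity or more symptoms of the disease under study, and 8.3.8 covers symptoms expected as a direct result of dyslipidemia. One event can fall under both.

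**Step 2: apply each rule to a serious event attributed to dyslipidemia.**

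| Section | Applies to | Exception if serious | Exception if IMP is stopped | Result |
|---|---|---|---|---|
| 8.3.7 | Events unequivocally due to progression | None | None | Not reported |
| 8.3.8 | Events unequivocally due to the disease | Yes | Yes | Reported |
| 8.3.4, progression sentence | Laboratory values only | None; SAEs are named in the exclusion | None | Not reported |
| 8.3.4, earlier list | Laboratory values and vital signs | Yes | Yes | Reported |
| 8.3.9 | All SAEs | Not needed | Not applicable | Reported, if the event counts as an AE |

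So 8.3.7 conflicts with 8.3.8, and 8.3.4 conflicts with itself.

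**Step 3: does 8.3.9 override 8.3.7?** Two readings are open. On the first, 8.3.9 is a general duty that prevails. On the second, 8.3.7 takes the event out of the AE category, Appendix B 2 makes AE status a condition for being an SAE, and 8.3.9 is never reached. The second reading has textual support, because 8.3.7 says of its disease-related symptoms that they are not AEs. The automated alert described in 8.3.9 also starts only when a site marks an AE as serious. The protocol does not say which section prevails.

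**Step 4: would an omitted event be recovered elsewhere?** In part. Deaths are captured through the End of Study form (SAP 3.3.1.3) and counted in disposition (SAP 4.1.1.1). Reasons for stopping treatment come from the end-of-treatment form (SAP 4.1.1.1). For a non-fatal serious event, neither document describes adjudication or separate event collection that would bring it into the SAE tables.

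**Step 5: size.** The documents give no expected rate of such events and no basis for guessing how often a site would omit one. With about 75 participants per arm (Protocol 6.3), one event is 1/75 = 1.3% of an arm. That is the weight of any single event. It says nothing about how likely an omission is.

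**The case against.** A reader might infer that hospitalised myocardial infarctions or strokes will be lost as disease progression and that the by-dose safety counts will be biased. The case against that reading is strong.

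- Section 8.3.7 is limited to events *unequivocally* due to progression, and its only example is a lipid rise. The protocol's background says hypercholesterolemia due to elevated LDL-C "is a major causal factor for IHD and IS in both the developed and the developing world". A major causal factor at population level does not make an individual infarction or stroke unequivocally due to progression of dyslipidemia.
- The intensity-scale text in Appendix B uses stroke as its example of an event that is an SAE once it meets the criteria, even if mild.
- Sections 8.3.8 and 8.3.9 both point towards reporting. A site has to read 8.3.7 in isolation to reach the opposite result.
- The progression sentence in 8.3.4 concerns laboratory values. It cannot remove a clinical event, and 8.3.4 makes accompanying signs or symptoms reportable.
- QT prolongation and blood-pressure elevation, listed in Protocol Table 2, are potential drug effects and not progression of dyslipidemia. The SAP also summarises both from measured data (4.6.5 and 4.6.6).
- Sites are blinded (Protocol 6.4.1), and nothing in the documents suggests that omission would differ by dose.

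All of this stands, and it rules out the stronger reading. It does not remove the contradiction. The exception is present in 8.3.8 and absent from 8.3.7, 8.3.4 gives opposite instructions within one section, and no rule of precedence is stated.

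**Conclusion.** The sections are inconsistent, and the inconsistency affects whether a serious event is reported. Followed literally and alone, 8.3.7 would keep a serious event attributed to dyslipidemia out of AE reporting and, through the definition in Appendix B 2, out of SAE reporting. The same holds for an event that leads to stopping the IMP. The supported consequence is a risk of inconsistent reporting between sites and a possible under-count of SAEs.

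This rests on two assumptions: that some investigator judges a serious event to be unequivocally due to progression, and that the site then applies 8.3.7 and not 8.3.8. Neither is shown to be likely. No magnitude can be given, and bias between dose arms is not demonstrated. The point merits correction because a stated rule points the wrong way for serious events and the protocol already contains the wording that resolves it.

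**What to change.** Reconcile the passages with the sponsor's own text. Add the exception from 8.3.8 ("unless they meet SAE criteria or lead to discontinuation of the IMP") to the last sentence of 8.3.7 and to the disease-progression sentence of 8.3.4. State in 8.3.7 that the exclusion is meant for changes such as lipid values, consistent with its own example.

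The cost is a few sentences in a protocol amendment or site letter, and possibly a few extra event reports. No assessment is added, and the SAP definitions can stay as they are.
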